### 4.3 CO-ENROLMENT GUIDELINES

Participants will not be permitted to co-enrol into other interventional studies for the duration of this study. However, there is an expectation that participants will be asked to co-enrol into other observational studies run by the CHERUB network, this participation is allowable.

## 5 TREATMENT OF PARTICIPANTS

### 5.1 IMP MANAGEMENT

All IMPs for the study will be stored and managed by a central pharmacy based at the Royal Free Hospital. They will be responsible for the storage and distribution of IMP to the clinical sites. Raltegravir has been donated by industry partners for use in the study and will be pre-shipped to clinical site pharmacies from where it will be dispensed to participants recruited. Dispensation of vaccines and vorinostat will take place at the Royal Free Hospital, when participants in Arm B attend for vaccination visits.

Raltegravir will be provided as a marketed product so MHRA-approved clinical trial labelling will be applied at the central pharmacy. Both the vaccines and vorinostat are unlicensed products so MHRA-approved clinical trial labelling will be applied by the manufacturer prior to shipping to RIVER central pharmacy.

Clinical trial IMP will be allocated to a participant on receipt of a completed prescription from the participant's clinician. On no account should any drug assigned to a participant be used by anyone else. Unused drug must be returned to the site pharmacy if a participant withdraws from treatment. The date that each participant started study treatment should be documented in the participant's clinical notes and added to the appropriate CRF.

All drug dispensed at and returned to the site pharmacy should be documented on a site accountability log, maintained by a named person (study pharmacist or research nurse). The designated study pharmacist/nurse will, on receipt of supplies prior to the commencement of the study, conduct an inventory and complete a receipt. Inventories will be conducted on an ongoing basis. Procedures for drug shipping, labelling, accountability and destruction will be detailed in the RIVER working practice documents. The RIVER Co-ordinating Centre will monitor drug accountability at site visits.

### 5.2 PRE-RANDOMISATION TREATMENT

#### 5.2.1 USE OF AN INTEGRASE INHIBITOR

Participants recently diagnosed (Cohort I) will receive combination antiretroviral therapy designed to reduce the plasma viral load as quickly as possible, hence the rationale for the preferred inclusion of raltegravir, an integrase inhibitor. Also, there is a hypothetical benefit for individuals receiving the latency reversing agent vorinostat that leads to viral transcription from the latent HIV reservoir, that the presence of an integrase inhibitor agent may better protect infection of uninfected CD4+ T-cells. However, there is no in vivo data to support this hypothesis. We therefore would prefer to include raltegravir as part of the combination antiretroviral therapy for all individuals at the time of randomisation.

However, in the absence of clear data individual participant preferences, viral genotype and co-morbidity, concomitant medication and clinical judgement can be used to ensure optimal viral suppression.

### 5.2.2 USE OF ART PRIOR TO ENROLMENT – COHORT I – RECENTLY DIAGNOSED

Participants who have taken Post-Exposure Prophylaxis (PEP) or Pre-Exposure Prophylaxis (PrEP) for prevention and prior to confirmation of primary HIV-1 infection are eligible for inclusion on the RIVER study. Participants in Cohort I – Recently diagnosed will either be ART naïve, have recently started an ART regimen after PHI diagnosis or have previously taken ART for prevention.

### 5.2.3 USE OF ART PRIOR TO ENROLMENT – COHORT II – PREVIOUSLY DIAGNOSED

For previously diagnosed participants who have already started on ART (Cohort II) only those that started at least 3 drug ART at PHI diagnosis, have been on at least 3-drug ART for  $\geq 22$  weeks and  $\leq 2$  years and are still on ART at screening will be eligible for randomisation.

If a participant is already on combination ART regimen that includes raltegravir this participant can proceed straight to screening and randomisation.

The preferred regimen prior to randomisation should contain raltegravir. For those participants that are not on raltegravir, and are willing to switch regimen, we recommend that once consent for the study has been taken, their combination ART be changed 6 weeks prior to randomisation to include raltegravir. During these 6 weeks, any toxicities associated with this switch in regimen should be monitored as per routine clinical guidelines. If the new regimen is well tolerated and the participant is compliant with their new regimen they can proceed to screening and randomisation. The participant should then continue on raltegravir the duration of the study.

However, where the use of raltegravir is contraindicated this can be substituted with ideally another integrase inhibitor. If however it is not possible to substitute this and the participant is eligible for randomisation they can join the study on their current ART regimen.

## 5.3 TREATMENT AT ENROLMENT/RANDOMISATION

Once eligibility for the study has been confirmed by the RIVER Co-ordinating Centre **all** participants will initiate or continue on appropriate combination ART (cART) preferably including raltegravir.

For ART naïve participants that start ART at enrolment the choice of the exact components of this will be based on HIV genotype, potential drug toxicities and interactions with any other concomitant medication and baseline HIV viral load. Usually at the time of acute HIV seroconversion with high viral load and high rates of skin rash and CNS symptoms, Truvada™ with a boosted Protease Inhibitor (PI) or an integrase inhibitor is the preferred regimen (Cohort I – Recently diagnosed).

For this study any BHIVA recognised appropriate ART is acceptable and will be individual participant-clinician choice. Preferably this will include the integrase inhibitor (INSTI), raltegravir (BID). Industry partners have donated this for the duration of the study with the plan to simplify treatment at the end of the study to standard therapy.

Patients who meet the eligibility criteria for randomisation (bloods taken at week 22 or at repeat visits for Cohort I [Section 3.3](#) and at screening for Cohort II [Section 3.4](#)) and have confirmed they are happy to proceed, will be randomised. At the randomisation visit, patients will be randomised to one of the two arms i.e. Arm A cART alone or Arm B to receive prime-boost vaccine and HDACi in addition to cART. Participants randomised to Arm B will have their post-randomisation week 00 and week 08 day 1 (PR00 and PR08-1) vaccine visits conducted at the Royal Free Hospital.

## 5.4 POST-RANDOMISATION (PR) TREATMENT

Once a participant has been randomised to the study the participant allocation will be confirmed by the RIVER Co-ordinating Centre. Participants in Arm B will be scheduled for their first vaccination at Royal Free Hospital as per treatment schedule see [Figure 5](#).

ARM	COMPONENT	DETAIL
Arm A: cART preferably including raltegravir	Combination ART (cART)	Likely consisting of an Nucleoside reverse-transcriptase inhibitor (NRTI) backbone i.e. Truvada® and raltegravir. cART is prescribed at enrolment/randomisation for the duration of the study Raltegravir dosage: oral 400mg tablet twice per day (BID). SmPC: Current version as posted to www.medicines.org.uk Marketing Authorisation Holder: Merck Sharp & Dohme Ltd
	Combination ART (cART)	Likely consisting of an Nucleoside reverse-transcriptase inhibitor (NRTI) backbone i.e. Truvada® and raltegravir. cART is prescribed at enrolment/randomisation for the duration of the study Raltegravir dosage: oral 400mg tablet twice per day (BID). SmPC: Current version as posted to www.medicines.org.uk Marketing Authorisation Holder: Merck Sharp & Dohme Ltd
	ChAdV63.HIVconsv (ChAd)	Dosage: $5 \times 10^{10}$ vp Administration: This dose is obtained by injecting 0.37ml of the vaccine at $1.35 \times 10^{11}$ vp/ml without dilution. This prime vaccination is administered intramuscularly (IM) into the deltoid muscle of the non-dominant arm within 1 week of randomisation at visit post-randomisation week 00 (PR00). Manufacturer: Clinical BioManufacturing Facility (CBF), Oxford, UK Storage: Vials are stored at between -70 and -90°C
	MVA.HIVconsv (MVA)	Dosage: $2 \times 10^8$ pfu Administration: This dose is obtained by injecting 0.23 ml of the vaccine IM at $8.6 \times 10^8$ pfu/ml without dilution. This boost vaccination is administered intramuscularly (IM) into the deltoid muscle of the non-dominant arm at post-randomisation week 8 Day 1 (PR08-1), 2 days prior to start of vorinostat. Manufacturer: Impfstoffwerk Dessau-Tornau (IDT) Biologika GmbH, Germany Storage: Vials are stored at between -70 and -90°C
Arm B: cART preferably including raltegravir + Vaccines + vorinostat	Vorinostat	Dosage: oral 400mg every third day from post-randomisation week 8 day 3 (PR08-3) to week 12 day 2 (PR12-2) inclusive. 10 doses in total. Administration: Vorinostat is administered orally with food. Participants should drink at least 2L fluid/day (on drug dosing days) to prevent dehydration and must report any excessive vomiting or diarrhoea; signs or symptoms of deep vein thrombosis (swelling and pain in a limb, shortness of breath, cough, pleuritic chest pain); unusual bleeding and seek medical attention. Manufacturer: Merck Sharp & Dohme Ltd Storage: at 20-25°C, excursions permitted between 15-30°C

Figure 5 RIVER Treatment Schedule – Cohort I – Recently diagnosed

[figure not shown]
[figure not shown]

Figure 6 RIVER Treatment Schedule – Cohort II – Previously diagnosed

## 5.5 CRITERIA FOR STARTING VORINOSTAT

Safety assessments will be undertaken to ensure it is safe for participants randomised to Arm B to receive vorinostat at post-randomisation week 08 day 3 (PR08-3). Only participants who meet these criteria will proceed to receive dosing with vorinostat.

Arm B participants must meet the following criteria at post-randomisation week 08 day 1 (PR08-1) in order to commence vorinostat 2 days later at post-randomisation week 08 day 3 (PR08-3):

1. Participant is willing to continue on combination antiretroviral therapy
2. Platelet count  $\geq 150 \times 10^9/L$
3. eGFR  $\geq 60^{**}$
4. Adequate haemoglobin (Hb  $\geq 12g/dL$  for males,  $\geq 11g/dL$  for females)
5. ALT  $< 5 \times ULN$
6. QTc interval normal, with normal defined as  $\leq 0.44s$  ( $\leq 440ms$ )

Any out-of-range results from the above indicate that the participant must not receive vorinostat. Participants in Arm B will then be followed for the rest of the study as per study visit schedule. Analysis of their data will be included as part of the intention to treat analysis of the primary study end point (see [Section 9.5](#))

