### 5.7.4 VORINOSTAT

In the event of a serious AE related to vorinostat the dosing will be terminated early. See below ([Section 5.8](#)) and in [Appendix II](#) for further guidance of toxicity management and dosing.

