## 5.8 DOSE MODIFICATIONS, INTERRUPTIONS & DISCONTINUATIONS

Toxicity will be managed in all randomised groups according to standard clinical practice. Blood tests additional to those described in the study schedule may be requested at any time for clinical management of the participant.

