**Table 5 Toxicity management during vorinostat dosing**

Toxicity	Grade	Vorinostat Dosing Action	Continuation
Non-haematological toxicity	Grade 1 or 2	No change unless due to impairment of QoL at discretion of Investigator (consider dose reduction as detailed below for Grade 2 toxicity)	Continue
Non-haematological toxicity	Grade 3 or 4	Cease treatment	Never
Anaemia, neutropenia or thrombocytopenia	Grade 1	No change	Continue
Neutropenia	Grade 2	Withhold vorinostat until returns to Grade $\leq 1$ .	If resolves to Grade $\leq 1$ , continue vorinostat at full dose. If on rechallenge recurs to Grade 2 or above, cease treatment. G-CSF is allowed at the clinician's discretion
Neutropenia	Grade 3 or 4	Cease treatment	
Febrile neutropenia	Grade 3 or 4	Cease treatment	
Anaemia or thrombocytopenia	Grade 2	Withhold vorinostat until returns to $\leq$ Grade 1	If resolves to $\leq$ Grade 1, continue vorinostat at full dose. If on rechallenge recurs to Grade 2 or above, cease treatment.
Anaemia or thrombocytopenia	Grade 3 or 4	Cease treatment	

Specific toxicity management in the setting of vorinostat dosing is provided in **Table 5** above. Grade 2 non-haematological toxicities, at the discretion of the treating clinician and with the agreement of the participant, can be managed with dose reduction of vorinostat to 300mg every third day. If the participant is intolerant of this reduced dose then the drug should be ceased all together, see **Section 5.7**.

All attempts must be made to avoid treatment interruptions; especially those for non-medical reasons e.g. 'drug holidays' or lost prescriptions. Treatment interruptions for medical reasons e.g. unable to have oral intake for whatever reason, are unavoidable and are permissible under this protocol as a protocol deviation. Every attempt should be made to limit the duration of treatment interruptions.

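### Section 5.5 sets vorinostat start limits for haemoglobin and platelets but none for neutrophils, although Table 5 holds the drug at Grade 2 neutropenia and ends it at Grade 3 or 4: a minor safety-consistency gap

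*Protocol*

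**What the plan says.** Section 5.5 of the protocol is the gate between the second vaccination and vorinostat: "Arm B participants must meet the following criteria at post-randomisation week 08 day 1 (PR08-1) in order to commence vorinostat 2 days later". The six criteria are willingness to stay on cART, platelets of at least 150 x 10^9/L, eGFR of at least 60, haemoglobin of at least 12 g/dL (men) or 11 g/dL (women), ALT below 5 times the upper limit of normal, and QTc of at most 440 ms. The gate is strict in both directions: "Only participants who meet these criteria will proceed to receive dosing with vorinostat", and "Any out-of-range results from the above indicate that the participant must not receive vorinostat". Anyone barred stays in follow-up and in the intention-to-treat analysis.

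Table 5 is headed "Toxicity management during vorinostat dosing". Its blood-count rows cover three conditions together at Grade 1, "Anaemia, neutropenia or thrombocytopenia", with no change of dose. At Grade 2 the action for neutropenia is "Withhold vorinostat until returns to Grade" 1 or lower; the full dose is then resumed, and the drug is stopped if Grade 2 or worse recurs. Grade 3 or 4 neutropenia ends treatment. Anaemia and thrombocytopenia have the same actions.

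Beyond these rules, section 5.8 says: "Toxicity will be managed in all randomised groups according to standard clinical practice". Section 5.7.4 refers to section 5.8 and Appendix II "for further guidance of toxicity management and dosing".

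**The concern.** The protocol treats three blood-count abnormalities as reasons to hold or stop vorinostat, but checks only two of them before the first dose. A man with haemoglobin of 11.9 g/dL, or anyone with platelets of 149 x 10^9/L, must not start. A participant with Grade 2, 3 or 4 neutropenia on the same sample meets every listed criterion.

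What is at stake is the safety of an individual participant. Vorinostat is not licensed for HIV, and these participants are otherwise well on suppressive treatment. There is also a handover at this step: the drug is dispensed at the central vaccination site at PR08-1, and the first dose is taken at the recruiting site two days later. An explicit list is useful there, because the person supervising the first dose may not be the person who ordered the blood count.

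**Working it through.** **1. The two rule sets side by side**

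| Count | Start limit in 5.5 | Grade 2 in Table 5 | Grade 3 or 4 in Table 5 |
|---|---|---|---|
| Haemoglobin | 12 g/dL men, 11 g/dL women | Hold until Grade 1 or lower | Cease |
| Platelets | 150 x 10^9/L | Hold until Grade 1 or lower | Cease |
| Neutrophils | None | Hold until Grade 1 or lower | Cease |

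Two of the three have a start condition. No earlier screen closes the gap: sections 3.3.1 to 3.3.3 and 3.4.1 to 3.4.2 contain no neutrophil threshold, and neither do the further conditions on receiving vorinostat in 5.7.1 to 5.7.3. The grade boundaries are in Appendix III, which is not in the available text, so no absolute count is given here.

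**2. How many doses the gap could allow**

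Dosing is every third day from PR08-3. Dose 1 falls in week 8 on day 3, dose 2 in week 8 on day 6, and dose 3 in week 9 on day 2, which is PR09-2.

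The columns of the assessment schedule are broken in the available text, so the visits with a full blood count are inferred. One at PR08-1 is implied because 5.5 cannot be applied without it. One at PR09-2 fits the blood volumes: a visit total of 86 ml equals 14 ml routine bloods + 32 ml immunology + 40 ml vorinostat virology, and SAP section 4.7 places the last two at PR09-2.

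- If Table 5 is applied to the known PR08-1 count as soon as dosing has begun: 1 dose.
- If nothing is done until the PR09-2 count, and its result is known before that day's dose: 2 doses.
- If the PR09-2 dose is taken before the result is back: 3 doses.

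**3. What an added criterion could cost in power**

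Inputs from Protocol 9.3: SD 0.4, baseline to follow-up correlation 0.5, PR16 to PR18 correlation 0.7, difference log10(2) = 0.301, two-sided alpha 0.05, 52 participants (26 per arm). Normal approximation.

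- Variance of the two-visit mean: 0.16 x (1 + 0.7)/2 = 0.136.
- Covariance with baseline: 0.5 x 0.16 = 0.08.
- Residual variance after baseline adjustment: 0.136 - 0.08^2/0.16 = 0.096, so SD 0.310.
- Standard error: 0.310 x sqrt(2/26) = 0.0859.
- Power: Phi(0.301/0.0859 - 1.96) = Phi(1.54) = 0.94, which reproduces the stated 94%.

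Now let one of the 26 in Arm B lose vorinostat and, at worst, show no effect at all. The expected difference becomes 0.301 x 25/26 = 0.289, and power is Phi(0.289/0.0859 - 1.96) = Phi(1.41) = 0.92.

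If all 60 enrolled were randomised and analysed (30 per arm), the standard error is 0.310 x sqrt(2/30) = 0.0800. Power is then about 0.96, falling to about 0.95 with a difference of 0.301 x 29/30 = 0.291.

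These figures price the fix. They are not evidence of the gap.

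**The case against.** The strongest reply is that a start list need not mirror an on-treatment table. Table 5 also ends vorinostat for any Grade 3 or 4 non-haematological toxicity, yet 5.5 names only eGFR, ALT and QTc among such measures. The list is a selection, it largely repeats the laboratory list for randomisation in 3.3.3, and the protocol gives reasons for it. Section 1.1.1.C describes anaemia and thrombocytopenia as dose-related and neutropenia as uncommon. Section 5.14.3 singles out thrombocytopenia for bleeding risk, and 7.2.1 ties haemoglobin to the large blood draws. This explains the focus on two counts and limits how often the gap could matter. It does not explain why neutropenia calls for a hold on one day and goes unchecked two days earlier.

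A second reply is clinical judgement: standard practice (5.8), treatment discontinuation (5.10), follow-up of abnormal results (6.3) and freedom to depart from protocol treatment (11.2.2). Section 5.5 also opens by stating that its purpose is safe dosing. This stands to the extent that dosing through a known low count is unlikely. But the same discretion exists for haemoglobin and platelets, and the protocol still gave them mandatory limits.

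A third reply is that a clinician could apply the neutropenia rows of Table 5 before the first dose. That would be sensible, but the table's title confines it to the dosing period and 5.5 does not refer to it.

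A reader might infer that an affected participant could go through all 10 doses unchecked. The documents do not support that: once dosing starts Table 5 applies, and section 6.3 ties blood-count monitoring to the dosing schedule. A reader might also infer that the protocol has no neutrophil start rule anywhere. That cannot be established without Appendix II; only its absence from 5.5 and the other available sections can be.

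**Conclusion.** The gap is real and minor. The listed start criteria admit a participant whose neutrophil count would, once dosing had begun, require vorinostat to be held or ended. Under the written rules the exposure is about one to three doses of 400 mg, and only if the clinician does not act on the PR08-1 count.

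The documents give no neutropenia rate at PR08-1, so no number of affected participants is claimed. It is expected to be very small: neutropenia is described as uncommon on vorinostat, and for Cohort I section 7.2.1 considers an effect on the blood system most unlikely. The primary analysis is unaffected, since participants are analysed as randomised whether or not they start the drug.

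The conclusion assumes that Appendix II contains no neutrophil start rule. If it does, the remaining point is only that 5.5 should cite it. The dose range assumes that the next full blood count after PR08-1 is at PR09-2.

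**What to change.** Add a seventh criterion to section 5.5: neutropenia no worse than Grade 1 (Appendix III) on the PR08-1 full blood count with differential. Grade 3 or 4 bars vorinostat. A Grade 2 count may be repeated once before the PR08-3 dose, and the participant may start if it has returned to Grade 1 or lower. The repeat matters because an outright bar at Grade 2 would be stricter than Table 5, which holds and then resumes. Anyone still out of range follows the existing 5.5 path: no vorinostat, continued follow-up, and inclusion in the intention-to-treat analysis. If the sponsor prefers to leave neutrophils out, 5.5 should say why.

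The cost is a change of protocol wording. The scheduled full blood count already includes the differential, so the only extra sample is the occasional repeat for a Grade 2 result. Rarely, a participant will lose vorinostat exposure; the worst-case loss for one such participant of 26 in Arm B is about two percentage points of power (94% to 92%).

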## 5.6 DISPENSING AND HANDLING

### 5.6.1 COMBINATION ART (cART)

All participants will be dispensed sufficient supplies of cART to ensure they have sufficient medication to last to the next study visit. Storage of ART is in accordance with the current SmPC for each agent. For Cohort I – Recently diagnosed suggested dispensing schedules are as follows (but may depend on time taken to meet eligibility criteria for randomisation):

- One-month supply at enrolment (week 0)
- Two-month supply at week 4, and
- Three-month supplies at week 12, randomisation visit and post-randomisation week 12.

For Cohort II – Previously diagnosed suggested dispensing schedules are as follows:

- Three month supplies at randomisation visit and post-randomisation week 12

### 5.6.2 RALTEGRAVIR

All participants will preferably be on a regimen that contains raltegravir at enrolment. All participants enrolled/randomised will be dispensed sufficient supplies to ensure they have sufficient medication to last to the next study visit. Raltegravir is supplied in marketed packs with 60 tablets per bottle. Store at 25°C (77°F); excursions permitted to 15°-30°C (59°-86°F).

Dispensing and handing procedures for raltegravir is as above for cART. Suggested dispensing schedule for both cohorts is as above for cART.

### 5.6.3 VACCINES

Irrespective of clinical site of enrolment, all vaccine study visits for the Arm B participants will be undertaken at one centralised vaccine site (Royal Free Hospital). The reason for this is to ensure uniform temperature and GMP procedures for vaccine procurement, storage, thawing and administration.

The first vaccination (ChAd) takes place at post-randomisation week 00 (PR00), within 1 week after randomisation, and the second vaccine (MVA), 8 weeks later, at PR week 08 day 1 (PR08-1). There is a visit window around the second vaccine of 7 days. On the days of vaccination, the vaccine will be allowed to thaw to room temperature and then administered within 1 hour of removal from the freezer. The vaccine will be administered intramuscularly (IM) over the deltoid region of the non-dominant arm. The investigator or study nurse will wear gloves and eye protection. During administration of the vaccines, medicines and resuscitation equipment will be immediately available for the management of anaphylaxis. The participant will remain in clinic for  $\geq 1$  hour of observation following the receipt of each vaccine. The participant will be contacted by phone by designated study personnel within 72 hrs of receipt of both vaccines to review any AEs. Participants should complete a 3 day vaccine diary following each vaccination.

In order to minimise dissemination of the recombinant vectored vaccine virus into the environment, the inoculation sites will be covered with a dressing after immunisation. This should absorb any virus that may leak out through the needle tracks. The dressings will be removed from the injection sites after 30 minutes and disposed of as genetically modified organism (GMO) waste by autoclave and then standard disposal, in accordance with current standard UK practice.

